5.6.1.3.3. Electrocardiograms

Descriptive statistics by visit and treatment group will be presented for each ECG parameter (including PR, QRS, QT, corrected QT interval [QTc], and QTc using Fridericia's formula [QTcF]) value and for change from baseline values.

An outlier analysis that will summarize the frequency and percentage of participants who meet any of the following outlier criteria will be performed:

- QT and QTcF interval > 450 msec
- QT and QTcF interval > 480 msec
- QT and QTcF interval > 500 msec
- QT and QTcF interval increases from Baseline > 30 msec
- QT and QTcF interval increases from Baseline > 60 msec

This outlier analysis will be performed for the PEP data only using the SS and separately for the aggregated PEP, ETP, and OLE Period (if applicable) data during the ALXN2050 treatment period using the ALXN2050-Treated Set.

Overall ECG results will also be classified as normal, abnormal not clinically significant, and abnormal clinically significant. A summary table will be provided for clinically significant abnormalities by visit and treatment group.

A by-participant listing of ECG results will be presented.

5.6.1.3.4. C-SSRS

The following categories are C-SSRS categories and have binary responses (yes/no):

- 1. Wish to be dead
- 2. Nonspecific active suicidal thoughts
- 3. Active suicidal ideation with any methods (not plan) without intent to act
- 4. Active suicidal ideation with some intent to act, without specific plan
- 5. Active suicidal ideation with specific plan and intent
- 6. Preparatory acts or behavior
- 7. Aborted attempt
- 8. Interrupted attempt
- 9. Nonfatal suicide attempt
- 10. Completed suicide

Self-injurious behavior without suicidal intent is also a C-SSRS outcome (although not suicide related) and has a binary response (yes/no).

Composite endpoints based on the above categories are defined as follows:

Suicidal Ideation (1-5): A yes answer to any one of the five suicidal ideation questions (categories 1-5) on the C-SSRS

Suicidal Behavior (6-10): A yes answer to any one of the five suicidal behavior questions (categories 6-10) on the C-SSRS

Suicidal ideation or behavior: A yes answer to any one of the ten suicidal ideation and behavior questions (Categories 1-10) on the C-SSRS.

For each of the 3 composite endpoints, as well as the self-injurious behavior without suicidal intent, the number and percentage of participants who experienced an event at Baseline and at least once during the PEP will be summarized by treatment group. The Baseline C-SSRS assessment includes both (a) lifetime assessment (for both the suicidal ideation and the suicidal behavior categories) and (b) 1 year prior to treatment.

A shift tabulation from Baseline will be produced by treatment group during the PEP. A separate shift tabulation will be produced against the 3 composite endpoints. The 3 groupings for the shift tables are as follows: (a) no suicidal ideation or behavior, (b) composite endpoint of suicidal ideation, and (c) composite endpoint of suicidal behavior. Each participant is counted in 1 cell only for each of the 2 tabulations. Participants with both suicidal ideation and suicidal behavior are included in the suicidal behavior category for the particular tabulation.

5.6.1.3.5. Other Observations Related to Safety

All results for neurological examination and pregnancy tests will be presented in a by-participant listing.

Virus serology test results at Screening, including human immunodeficiency virus (HIV)-1, HIV-2, hepatitis B virus, and hepatitis C virus, will be presented in a by-participant listing only.

5.6.2. Safety Analyses at Analysis 2 (Week 34)

All outputs for safety outcomes during the first 34 weeks and aggregated safety summary, including additional OLE Period data during the ALXN2050 treatment period, will be based on the ALXN2050-Treated Set, unless otherwise specified. Baseline is defined as the last available assessment prior to the first dose of study intervention. Baseline for Groups 3a and 3b is the last available assessment prior to the first dose of study intervention during the PEP.

5.6.2.1. Extent of Exposure

The same analyses as specified in Section 5.6.1.1 will be performed using the first 34 weeks of data (PEP and ETP) and the SS.

5.6.2.2. Adverse Events

AEs during the respective period for each group will be analyzed and reported in terms of TEAEs, which are defined as follows:

• Groups 3a and 3b: any AEs that started or worsened in severity on or after the first dose of study intervention in the ETP and before the first dose in the OLE Period or, if discontinued before the OLE Period, before the last dose + 30 days. The same analyses as specified in Section 5.6.1.2 will be performed using the first 34 weeks of data (PEP and ETP) and ALXN2050-Treated Set. Additional analyses will be performed, including the aggregated PEP, ETP, and OLE Period AE data up to the cutoff date by dose received ("ALXN2050 180 mg bid" and "ALXN2050 120 mg bid") at the time of the AE using the ALXN2050-Treated Set.

5.6.2.3. Additional Safety Assessments

The same analyses as specified in Section 5.6.1.3 will be performed using the first 34 weeks of data (PEP and ETP).

Additional safety data collected by study visit during the OLE Period (as specified in Section 5.6.1.3) will be listed and summarized by dose level, which is the dose received ("ALXN2050 180 mg bid" and "ALXN2050 120 mg bid") at the specific visit during the OLE Period.

5.7. Other Analyses

5.7.1. PK Analyses

For both of Analysis 1 (Week 8) and Analysis 2 (Week 34), the SS will be used for PK concentration listings and individual figures, and the PK set will be used for PK parameter listings, all summary tables, and mean figures.

5.7.1.1. Data Handling

Plasma concentrations that are below the limit of quantification (BLQ) will be treated as 0 for calculation of descriptive statistics. When all concentrations are BLQ for a timepoint, the mean will be presented as BLQ, and the SD and coefficient of variation (CV) will be reported as not applicable; otherwise, the calculated mean will be presented.

For PK parameter calculations, BLQ values will be treated as 0.

Data rounding specifications for PK data are documented in the PK tables, listings, and figures (TLF) shells.

5.7.1.2. Plasma PK Concentrations

Blood samples for the analysis of concentrations of ALXN2050 in plasma for each of the treatments will be collected at the following timepoints:

- PEP of 8 weeks (Day 1 to Week 8): predose on Days 1, 29, and 57 and at 2 and 4 hours postdose on Days 1 and 57.
- ETP of 26 weeks (Weeks 9 to 34): predose on Days 85, 113, 183, and 239 and at 2 and 4 hours postdose on Days 85 and 113.

Available individual plasma concentrations of ALXN2050 for each treatment, at the time of each analysis, will be presented in data listings and summarized separately using descriptive statistics (N, n [nonmissing values within the population], arithmetic mean, SD, CV percentage [CV%], median, minimum, and maximum) by period (PEP and ETP), treatment group, day, and scheduled timepoint. Individual plasma concentrations of ALXN2050 will be plotted for each participant by actual time (in days) continuous for both periods on both linear and semilogarithmic scales. Mean plasma concentrations of ALXN2050 versus nominal time (in days) will be plotted continuous for both periods on both linear and semilogarithmic scales and with actively treated groups overlayed on the same plot.

Plasma PK concentrations of ALXN2050 will be reported to 3 significant figures in summary statistics except for CV%, which will be reported to 1 decimal place, and N and n, which will be reported as an integer.

5.7.1.3. Plasma PK Parameters

The principal PK parameters for each participant will be derived using SAS Version 9.4 or higher. The following PK parameters will be determined for ALXN2050, where data permit:

| C _{max} | Maximum observed concentration | |
|---------------------|---|--|
| C _{trough} | Pre-dose concentration prior to the administration of the next dose | |

Plasma PK parameters of ALX2050 will be presented in data listings and summarized separately using descriptive statistics (number of observations, arithmetic mean, SD, CV, geometric mean, geometric CV, median, minimum, and maximum) by period (PEP and ETP), treatment group, and day.

5.7.2. PD Analyses

For both Analysis 1 (Week 8) and Analysis 2 (Week 34), the SS will be used for all PD listings and individual absolute and change from baseline activity/concentration-time profiles, and the PD set will be used for PD summary tables and mean figures.

Baseline is defined as the last available assessment before the first dose of study intervention (predose Day 1 or Screening, whichever is the later and available). Baseline for Groups 3a and 3b is the last available assessment prior to the first dose of study intervention during the PEP.

5.7.2.1. Data Handling

Missing concentrations will be excluded from all calculations and PD analyses.

Data rounding specifications for PD data are documented in the PK TLF shells.

5.7.2.2. Serum AP Activity and Plasma Bb Concentrations

Serum AP Activity

Blood samples for the analysis of serum AP activity over time for each of the treatments will be collected at the following timepoints:

- PEP of 8 weeks (Day 1 to Week 8): predose on Days 1, 29, and 57 and at 2 and 4 hours postdose on Days 1 and 57.
- ETP of 26 weeks (Weeks 9 to 34): predose on Days 85, 113, 183, and 239 and at 2 and 4 hours postdose on Days 85 and 113.

Plasma Bb Concentrations

Blood samples for the analysis of plasma Bb concentrations for each of the treatments will be collected at the following timepoints:

- PEP of 8 weeks (Day 1 to Week 8): predose on Days 1, 29, and 57 and at 2 hours postdose on Day 1.
- ETP of 26 weeks (Weeks 9 to 34): predose on Days 85, 113, 183, and 239.

The predose sample will be classified as the baseline value. Individual absolute values and change from Baseline in serum AP activity and plasma Bb concentrations will be presented in data listings and summarized separately using descriptive statistics (N, n [nonmissing values within the population], arithmetic mean, SD, CV%, median, minimum, and maximum) by group, period (PEP and ETP), day, and scheduled timepoint.

Individual absolute values and change from Baseline in serum AP activity and plasma Bb concentrations will be plotted for each participant by actual time (in days). Mean change from Baseline in serum AP activity and plasma Bb concentrations will be plotted by nominal time (in days) continuous for both periods and with all groups overlayed on the same plot.

Serum AP activity and plasma Bb concentration will be reported to 3 significant figures in summary statistics except for CV%, which will be reported to 1 decimal place, and N and n, which will be reported as an integer.

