- g To reduce the risk of meningococcal infection (*Neisseria meningitidis*), all participants must be vaccinated against meningococcal infection within 3 years or before the administration of study intervention on Day 1. Participants who initiate study intervention treatment less than 2 weeks after receiving a meningococcal vaccine must receive treatment with appropriate prophylactic antibiotics until at least 2 weeks after vaccination.
- h Pregnancy tests must be performed on all participants of childbearing potential at the specified time points. Serum pregnancy test will be performed at the Screening, ED, and EOS visits; urine pregnancy tests will be performed locally at all other specified time points. Additional pregnancy tests (urine or serum) may also be performed at any in-clinic visit at the Investigator's discretion.

i Follicle-stimulating hormone may be obtained at the Screening Visit to confirm postmenopausal status in female participants who are considered postmenopausal ONLY. This test is not needed for men and will not be conducted in women of childbearing potential.

- j All participants who continue to meet all inclusion criteria and none of the exclusion criteria and have been cleared for randomization by the Investigator will be centrally randomized via an interactive response technology.
- k Participants randomized to placebo will be further randomized to 1 of the 2 active treatment groups (ie, ALXN2050 120 or 180 mg bid).
-  Ensure kit and lot number are recorded on the drug accountability log.
- m Dosing is by mouth bid throughout the PEP.
- n Participants will receive newly dispensed study intervention at Week 8 and the first dose will be administered during this visit. The participant will then continue at home dosing per protocol.
- o The QMG assessment should be performed by a properly trained Clinical Evaluator (preferably the same evaluator) throughout the study. If a participant is taking a cholinesterase inhibitor, the dose must be withheld for at least 8 h prior to the assessment and, whenever possible, the time from the last dose to the QMG assessment should be kept similar between visits.

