#### Table 3: Schedule of Activities (Extended Treatment Period)

Period	Extended Treatment Period a												
Study Year					Y	ear 1							
Study Day (D)	D64	D71	D78	D85	D92	D99	D106	D113	D183	D239	ED b	CDc	EOS b
Study Week (W)	W9	W10	W11	W12	W13	W14	W15	W16	W26	W34	NA	NA	NA
Visit Type	Phone call	Phone call	Phone call	In- clinic	Phone call	Phone call	Phone call	In- clinic	In- clinic	In- clinic	In- clinic	In- clinic	In- clinic
Study Window (days)	NA	NA	NA	±3	NA	NA	NA	±3	±3	±3	NA	NA	±2
Safety Laboratory Tests o													
Serum pregnancy p											Х		Х
Urine pregnancy p				Х				Х	Х	Х		Х	
Clinical chemistry				Х				Х	Х	Х	X	Х	
Hematology				Х				Х	Х	Х	Х	Х	
Coagulation panel				Х				Х	Х	Х	Х	Х	
Urinalysis				Х				Х	Х	Х	Х	Х	
PK/PD Tests q													
РК				Xr				Xs	Xr	Xr		Xr	
PD: AP activity and Bb t				Х				Х	Х	Х		Х	
Biomarker Tests													
Anti-AChR antibody				Х				Х	Х	Х	X	Х	
Factor D, C3, CP activity, nongenetic exploratory biomarkers (eg, MuSK, LRP4) u				X				х	х	x	Х	X	
Other				Х									
Concomitant medication	X	Х	Х	Х	Х	Х	Х	Х	Х	Х	X	Х	Х
Nonpharmacologic treatments and therapies	Х	Х	Х	Х	Х	X	X	X	Х	X	Х	X	Х

a The ETP begins at the Day 57 (Week 8) Visit after all assessments of the visit are performed, but before the administration of ALXN2050 in the clinic and postdose PK/PD sampling.

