- Extended Treatment Period of 26 weeks (Week 8 to Week 34) The ETP begins at the Day 57 (Week 8) Visit after all assessments of the visit are performed, but before the administration of ALXN2050 in the clinic and postdose PK/PD sampling. During this timeframe, participants in the ALXN2050 180 mg bid and ALXN2050 120 mg bid groups will continue taking the dose to which they are randomized. Participants in the placebo group will be stratified by MG-ADL total score at baseline (pre-placebo) and re-randomized in a 1:1 ratio to either ALXN2050 180 mg bid (Group 3a) or ALXN2050 120 mg bid (Group 3b). All participants will receive active study intervention; however, the actual dosage of ALXN2050 will be blinded to participants, Investigators, and site personnel. Visits at Weeks 9, 10, 11, 13, 14, and 15 will be conducted via telephone contact (Table 3). Participants will present for in-clinic visits at Weeks 12, 16, 26, and 34. The first dose of study intervention during in-clinic visit days will be administered by the site personnel. The participant will take the second dose of study intervention at home. The last visit for the ETP will be the Week 34 Visit.
- Open-label Extension Period of up to approximately 1.5 years (Week 34 to Week 117) – The OLE Period begins at the Day 239 (Week 34) Visit after all assessments of the visit are performed, but before the administration of ALXN2050 in the clinic and postdose pharmacokinetics/pharmacodynamics (PK/PD) sampling. During this timeframe, all participants will receive active study intervention. If an optimal dose of ALXN2050 has been identified, all participants will be switched to this optimal dose, as long they have completed the first 34 weeks of treatment. However, the actual dose of ALXN2050 will continue to be blinded to participants, Investigators, and site personnel during this study period until they are switched to the

optimal dose, if one is identified during the study. Participants will return to the clinic approximately every 3 months as indicated in the SoA (Table 4). The first dose of study intervention during in-clinic visit days will be administered by the site personnel. The participant will take the second dose of study intervention at home. The last visit for the OLE Period is the EOS Visit.

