5. STATISTICAL ANALYSES

5.1. General Considerations

Summary statistics will be computed and displayed by visit, by treatment group, and overall, where applicable. The summary statistics for continuous variables will include, but will not be limited to, the number of participants, mean, SD, minimum, median, and maximum. For categorical variables, frequencies and percentages will be presented.

Inference from efficacy analyses will be based on a 2-sided type I error rate of 10% unless stated otherwise. No multiplicity adjustment will be implemented. Statistical analyses will be performed using the Statistical Analysis Software (SAS[®]) Version 9.4 or higher.

Medications will be coded using the World Health Organization Drug Dictionary (WHO DD; March 2021 or higher). Therapies will be coded using Medical Dictionary for Regulatory Activities (MedDRA; Version 24.0 or higher).

AEs will be coded by primary System Organ Class (SOC) and Preferred Term (PT) using MedDRA (Version 24.0 or higher).

5.1.1. Data Presentation for the First Analysis at Week 8

Data summaries for the analyses on the PEP data will be presented by 3 treatment groups ("Group 1: ALXN2050 180 mg bid", "Group 2: ALXN2050 120 mg bid" and "Group 3: Placebo"). Baseline is defined as the last measurement on or prior to the first dose of study intervention. For analysis including data beyond week 8, data summaries will be presented by 5 treatment groups ("Group 1: ALXN2050 180 mg bid", "Group 2: ALXN2050 120 mg bid", "Group 3: Placebo", "Group 3a: ALXN2050 180 mg bid" and "Group 3b: ALXN2050 120 mg bid"). Placebo group may be dropped for some of the analyses as specified in the respective sections. For all groups other than Groups 3a and 3b, baseline is defined as the last measurement on or prior to the first dose of study intervention. For Group 3a and 3b, two baselines will be defined for efficacy analysis: the PEP baseline is defined as the last measurement on or prior to the first dose of the PEP (primary baseline) and the ETP baseline is defined as the last measurement on or prior to the first dose of the Group 3a and 3b.

5.1.2. Data Presentation for the Second Analysis at Week 34

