5.5.1.1. Dual Responder in MG-ADL and QMG

The FAS will be used for this analysis.

Responder is defined as participants with both an MG-ADL total score reduction of ≥ 2 points and a QMG total score reduction of ≥ 3 points in any 4 consecutive weeks during the first 8 weeks and who did not receive rescue therapy. The number and proportion of responders will be summarized by treatment group. The exact (Clopper-Pearson) 90% CI for each treatment group will be presented. The differences in proportions between each of the ALXN2050 dose groups (180 mg bid or 120 mg bid) and the placebo group will be presented, along with 2-sided 90% CIs using the Chan and Zhang method (Chan, 1999). The same intercurrent event handling approach will be followed as specified in the primary analysis of the primary endpoint in Table 1.

5.5.1.2. Proportion of Participants With 2-Point Improvement in the MG-ADL Total Score for 4 Consecutive Weeks and Who Did Not Use Rescue Therapy

The FAS will be used for this analysis.

This analysis includes MG-ADL data of the first 8 weeks (Groups 1, 2, and 3) and Week 8 to 16 data for Groups 3a and 3b participants who have completed Week 16 assessment or discontinued prior to Week 16 by the data cutoff date.

The proportion of participants with at least a 2-point improvement in the MG-ADL total score for 4 consecutive weeks (measured from Day 1 [PEP baseline] to Week 8 for Groups 1, 2, and 3 and from Week 8 [ETP baseline] to Week 16 for Groups 3a and 3b) and who did not receive any rescue therapy will be summarized. The exact (Clopper-Pearson) 90% CI for each group will be presented. Summaries using the PEP and ETP baselines will be both presented for Groups 3a and 3b. The same intercurrent event handling approach will be followed as specified in the primary analysis of the primary endpoint in Table 1.

For Groups 3a and 3b, this endpoint will be summarized in a shift table presenting the shift in responder status from the first 8 weeks to Weeks 8 to 16 (using the PEP and ETP baselines separately for Week 8 to 16 responder status). The observed frequencies and percentages, together with an exact (Clopper-Pearson) 90% CI for the true percentage of responders, will be presented for the first 8 weeks and Weeks 8 to 16 separately. The difference in percentages of responders (Weeks 8 to 16 [first 8 weeks]) and corresponding 90% CI for the true difference will also be presented for each group.

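### The SAP lists the Day 57 2 h and 4 h PK and AP activity samples under the PEP, so the placebo arm's first on-drug values most directly read as placebo results

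*SAP*

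**What the plan says.** **SAP, sampling lists.** Sections 5.7.1.2 (PK) and 5.7.2.2 (AP activity) carry the same PEP entry: "predose on Days 1, 29, and 57 and at 2 and 4 hours postdose on Days 1 and 57". The ETP entry in both sections is headed Weeks 9 to 34 and names Days 85, 113, 183 and 239. Day 57 therefore appears only under the PEP.

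**SAP, tabulation.** PK concentrations are summarised "by period (PEP and ETP), treatment group, day, and scheduled timepoint" and AP activity "by group, period (PEP and ETP), day, and scheduled timepoint". Section 5.1.1 states: "Data summaries for the analyses on the PEP data will be presented by 3 treatment groups", one of which is placebo. The same section gives five groups, with 3a and 3b identified by dose, for analyses that reach past Week 8. Section 5.1.2 gives five groups for PK/PD at Analysis 2.

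**Protocol.** Section 4.1 and Table 3 footnote a start the ETP at the Day 57 visit, once the visit's assessments are done "but before the administration of ALXN2050 in the clinic and postdose PK/PD sampling". Section 8.11.7 re-randomises the placebo arm to 120 mg or 180 mg at Week 8. Table 2 footnote n adds: "Participants will receive newly dispensed study intervention at Week 8 and the first dose will be administered during this visit". Table 2 itself shows the Day 57 peak PK and AP samples (footnotes x and z) in a column headed Primary Evaluation Period.

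**SAP Addendum 1.2.** PK parameters, population PK and exposure-response are dropped, and the other PK/PD outputs stay. Exposure and adverse events are split into PEP data by Groups 1, 2 and 3, and ALXN2050-treated data by Groups 1, 2, 3a and 3b. No such split is stated for PK/PD.

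**The concern.** For a participant in the placebo arm, the Day 57 predose sample is the last one off drug, and the 2 h and 4 h samples are the first ones on drug. A period label that keeps all three together joins off-drug and on-drug values in one group.

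If the tables follow the SAP's period label, the placebo row at Day 57 would show ALXN2050 concentrations, and any AP inhibition after a first dose, with 120 mg and 180 mg recipients pooled. The AP mean plot overlays all groups, so its placebo line would carry the same on-drug points. The PK mean plot overlays actively treated groups only, so Groups 3a and 3b would lack their first-dose points there. These outputs serve the protocol's PK/PD objective and remain in the final report.

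**Working it through.** **1. Where the boundary falls.** Day 57 is (57 − 1)/7 = 8.0 weeks, the visit shared by the PEP and the ETP. The texts treat the postdose samples as follows.

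| Source | Day 57 2 h and 4 h PK and AP samples |
|---|---|
| Protocol 4.1; Table 3 footnote a | After the ETP has started; postdose PK/PD sampling is named |
| Protocol Table 2 | In a PEP column |
| SAP 5.7.1.2 and 5.7.2.2 | In the PEP list; ETP list begins at Week 9 |
| SAP 5.6.1.2 and 5.6.2.2 (treatment-emergent AEs) | Not about samples, but the PEP ends, and 3a/3b begin, at the first ETP dose |
| SAP 6.4 (changes to protocol-planned analyses) | No change declared |

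Under the AE rules, an event in the placebo arm one hour after the Day 57 dose belongs to Group 3a or 3b. Under 5.7.1.2, a PK sample drawn an hour later belongs to the PEP.

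**2. From period to group label.** Period is a tabulation variable for both assays. PEP data go into three groups, including placebo. Neither 5.7.1.2 nor 5.7.2.2 removes placebo from the tables, and the PK and PD Analysis Sets (SAP 4) do not exclude placebo participants. The introduction to SAP 5.5, written for the exploratory endpoints, equates Group 3 with the PEP of the placebo arm and Groups 3a/3b with its ETP and OLE. Hence period = PEP leads most directly to Group 3. This step is an inference; no sentence assigns these values to placebo.

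**3. Size, from planned numbers (70 participants, 2:1:2).**
- Placebo arm: 70 × 2/5 = 28. Re-randomised 1:1: 28/2 = 14 each in Groups 3a and 3b.
- Affected table rows: 2 timepoints × 2 assays = 4.
- Affected values: 28 × 2 = 56 per assay at most, if all reach Week 8 with no missing sample.
- Bb: 0, because it has no Day 57 postdose sample in the SAP or the protocol.

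**4. How far the placebo row could move.** The documents give no first-dose AP inhibition in gMG. As an assumption, with mean inhibition x, the row would show 100 × (1 − x)% of baseline: 100% at x = 0, 70% at 0.3, 40% at 0.6 and 10% at 0.9.

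**5. What relabelling changes.** SAP 5.7.2 already sets the PD baseline for Groups 3a and 3b at the PEP baseline, so no individual change from baseline moves. No placebo control exists at Day 57 postdose under any label.

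**The case against.** The strongest reply is that the SAP also provides a five-group display (5.1.1 for data past Week 8, 5.1.2 for PK/PD at Analysis 2), and the PK/PD outputs run across both periods. On that view the mapping is unspecified rather than wrong. This stands in part: dose-labelled columns for 3a and 3b exist, and a programmer could use them. But no supplied text sends the Day 57 postdose values there, and the period label points the other way.

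The cited entries are also sampling schedules that mirror Protocol Table 2, so the tension begins inside the protocol. That is fair. Even so, Section 4.1 and Table 3 footnote a address postdose PK/PD sampling expressly, whereas Table 2 does so only by a column heading.

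Table specifications sit in a separate data presentation plan, and an addendum dated 20 Dec 2023 covers the Week 8 analysis. Neither was available, and either may settle the labels.

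A reader might infer that the SAP contradicts its own efficacy boundary, for example "from Week 8 [ETP baseline] to Week 16 for Groups 3a and 3b" in 5.5.1.2, or the Week 8 to 34 windows in 5.5.2.5 and 5.5.2.7. It does not: these work at visit level and do not separate predose from postdose. SAP 6.1.2 defines a baseline, not a reporting period. Only the AE rules set a boundary at the dose.

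**Conclusion.** The period assignment in SAP 5.7.1.2 and 5.7.2.2 conflicts with the ETP start in Protocol 4.1 and Table 3 footnote a, and should be corrected. The placebo label is the most direct consequence, not an explicit instruction. A reader might infer that the SAP orders on-drug values to be reported as placebo; the five-group provisions prevent that conclusion.

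The effect is confined to four descriptive table rows, the Day 57 postdose points on the AP mean plot, and missing 3a/3b first-dose points on the PK mean plot. Up to 28 planned placebo participants are involved, about 14 per dose. These are planned numbers before dropout, and actual numbers are not in the documents.

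A reader might also infer that half of the first-dose participants at 120 mg (14 of 14 + 14 = 28) and a third at 180 mg (14 of 28 + 14 = 42) would lose their dose label. Those shares assume both the placebo reading and full planned retention, so they are not established.

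Efficacy, Bb, predose rows, listings, individual plots and every individual value are unaffected. Since population PK and exposure-response are dropped, no remaining analysis in the supplied text uses these rows for dose selection.

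**What to change.** In SAP 5.7.1.2 and 5.7.2.2:

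- Keep only the Day 57 predose sample in the PEP.
- Assign the Day 57 2 h and 4 h PK and AP values to the ETP, under Groups 1, 2, 3a and 3b, with no placebo row at those timepoints. This matches the first-ETP-dose boundary of the AE rules.
- At a minimum, relabel only the placebo arm's values to 3a and 3b, with a footnote. This avoids splitting one visit's trough and peak samples across two periods for Groups 1 and 2, whose treatment does not change.
- Add a note reconciling the PEP heading of Protocol Table 2 with Table 3 footnote a. If the table shells or the 20 Dec 2023 addendum already map these samples, cite them.

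The cost is SAP wording and a label mapping in programming. No new data are needed and no individual value changes.

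Separately, and minor: both SAP sections list 2 h and 4 h PK and AP samples on Day 85, whereas Protocol Table 3 (footnotes r and t) has Week 12 as predose only. The two should be reconciled.
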